7.1.8 Injection Site Reaction (ISR) Diary

The ISR Diary will be completed by the subject beginning on the day of treatment with VOLUMA™ and for daily for 4 weeks.

If Touch-up treatment is received at Visit 5, the initial ISR Diary provided at Visit 4 will be collected. A new ISR Diary will be dispensed and started at touch-up treatment. Four weeks of ISR will be collected after the last VOLUMA™ treatment. An example of the ISR Diary is available in *Appendix 11*.

Clinical Study Protocol: CMO-MA-FAS-0513

7.2 EFFICACY MEASURES

7.2.1 Allergan Loss of Jawline Definition Scale

The ALJDS is an Investigator assessment of jawline contour measured by a 5-point scale (see *Appendix 3*). The Investigator will use the ALJDS to perform a live assessment of the subject at the visits specified in *Table 1.1: Schedule of Visits and Procedures*. Photographic images will be collected to capture the subject status at the time of the live assessments.

A third party Independent Reviewer (IR) will use the photographic images collected during the subject visits to evaluate jawline definition using the ALJDS.

7.2.2 Clinician-Reported Submental Fat Rating Scale (CR-SMFRS)

The CR-SMFRS is an Investigator assessment measured on a 5-point scale (see *Appendix 4*). The Investigator will use the CR-SMFRS to perform a live assessment of the subject at the visits specified in *Table 1.1: Schedule of Visits and Procedures*. Photographic images will be collected to capture the subject status at the time of the live assessments.

7.2.3 Patient-Reported Submental Fat Rating Scale (PR-SMFRS)

The PR-SMFRS is a subject assessment measured on a 5-point scale (see *Appendix 5*). The subject is instructed to position his or her head as described for the CR-SMFRS assessment and is asked to complete a questionnaire about the area under their chin using a mirror to help them. The subject completes a live assessment at the visits specified in *Table 1.1: Schedule of Visits and Procedures*. Photographic images will be collected to capture the subject status at the time of the live assessments.

7.2.4 Submental Skin Laxity Grade (SMSLG)

The SMSLG is based on the Investigator's clinical evaluation of the subject, including palpation of the chin and neck area, oblique and profile views of the chin and neck, as well as observation of the pronation, supination, and lateral movement of the head (see *Appendix 6*). The Investigator will use the SMSLG to perform a live assessment of the subject at the visits specified in *Table 1.1: Schedule of Visits and Procedures*. Photographic images will be collected to capture the subject status at the time of the live assessments.

7.2.5 FACE-Q™ Questionnaires

The FACE-Q™ modules were designed to assess the impact of treatment from the subject's perspective, specifically the impact of treatment from the subject's appraisal of the area under their chin (see *Appendix 7*), neck (see *Appendix 8*), and satisfaction with lower face and jawline (see *Appendix 9*).

7.2.5.1 Appraisal of Area Under Chin

The subject will assess satisfaction using the 5 items on the Appraisal of Area Under Chin module of the FACE-Q™ questionnaire. The responses to the 5 items are combined to create a scale score that ranges from 0 (worst) to 100 (best).

Clinical Study Protocol: CMO-MA-FAS-0513

7.2.5.2 Appraisal of Neck

The subject will assess satisfaction using the 10 items on the Neck module of the FACE-Q™ questionnaire. The responses to the 10 items are combined to create a scale score that ranges from 0 (worst) to 100 (best).

7.2.5.3 Satisfaction of Lower Face and Jawline

The subject will assess satisfaction using the 5 items on the Satisfaction of Lower Face and Jawline module of the FACE-Q™ questionnaire. The responses to the 5 items are combined to create a scale score that ranges from 0 (worst) to 100 (best).

7.2.6 Global Aesthetic Improvement Scale (GAIS) Questionnaires

7.2.6.1 GAIS Investigator

Investigator's assessment of global facial aesthetic improvement as measured by the 5-point GAIS (see *Appendix 10*).

7.2.6.2 GAIS Subject

Subject's assessment of global facial aesthetic improvement as measured by the 5-point GAIS (see *Appendix 10*).

[REDACTED]

8 DISCONTINUATION CRITERIA

8.1 DISCONTINUATION OF THE STUDY

The Investigator or Allergan, may terminate the Investigator's participation in this study after submission of a written notice. Allergan may terminate the study at any time for any reason.

8.2 DISCONTINUATION OF SUBJECTS

A subject may voluntarily withdraw or the Investigator may withdraw the subject at any time without prejudice to the subject's future medical care by the Investigator or institution. It is the responsibility of the site Investigator to discontinue a subject's participation when the subject's health or wellbeing is threatened by continuation in the study.

Clinical Study Protocol: CMO-MA-FAS-0513

For any subjects who withdraw from the study, the date and reason for withdrawal will be recorded on the eCRF. If an AE or ISR is ongoing at the time of the withdrawal, the Investigator will attempt to follow the subject until the AE or ISR has resolved or stabilized.

8.2.1 Withdrawal Criteria

The following circumstances shall result in a subject's discontinuation from the study:

- If a subject becomes pregnant,
- Subject is lost to follow-up. Subjects may be withdrawn if they do not return for follow-up visits. If a subject fails to return for one or more scheduled study visits, the Investigator will attempt to contact the subject to determine and document the reason the subject has failed to return and to encourage compliance with the study visit schedule.

The following circumstances may result in a subject's discontinuation from the study. Investigator should contact Allergan prior to withdrawal of the subject.

- AEs or serious adverse events (SAEs) that render the subject unable to continue study participation
- Protocol violation
- Non-compliance with study requirements
- During the study, the subject meets any of the Exclusion Criteria listed in section 4.3
- Progressive injury (at the discretion of the Investigator)
- There are changes in the subject's condition that render the subject unacceptable for further participation in the judgment of the Investigator
- A subject is unable to physically or mentally tolerate the use of the test treatment
- Discretion of Investigator

The reason for withdrawal shall be documented in the source documents and in the eCRF.

9 ADVERSE EVENTS

Throughout the course of the study (from the date of informed consent), all AEs will be monitored and recorded in source documents and on the AE eCRF. If an AE occurs, the first concern will be the safety of the study participant. All AEs related to study treatments or procedures will be followed until resolved or stabilized based on the Investigator's clinical judgment or until follow-up is no longer possible.

Clinical Study Protocol: CMO-MA-FAS-0513

9.1 DEFINITIONS

9.1.1 Adverse Events (AE)

9.1.1.1 Drug

An AE is any untoward medical occurrence in a subject administered a pharmaceutical product and that does not necessarily have a causal relationship with this treatment. An adverse event can therefore be any unfavorable and unintended sign (including an abnormal laboratory finding), symptom, or disease temporally associated with the use of a medicinal (investigational) product, whether or not related to the medicinal (investigational) product.

AEs will be assessed and documented, as appropriate, throughout the study (i.e., after informed consent has been obtained). At each visit, the Investigator will begin by querying for adverse events by asking each subject a general, non-directed question such as “How have you been feeling since the last visit?” Directed questioning and examination will then be done as appropriate. All reported adverse events will be documented on the AE eCRF.

9.1.1.2 Medical Device

An AE is defined as any undesirable physical, psychological or behavioral effect experienced by a subject during his/her participation in a study, in conjunction with the use of the device, whether or not it is considered related to the procedure or the product. AEs may include, but are not limited to, subjective or objective symptoms spontaneously offered by the subject, solicited via subject interviews, uncovered by review of concomitant medications, therapies, and treatments and/or observed by the Investigator. The Investigator will record the description (sign, symptom and diagnosis), location, onset, resolution, seriousness, severity, cause, and action taken for any event on the AE eCRF. To maintain study blind, the Evaluating Investigator must not be present during the safety evaluations.

Disease signs and symptoms that existed prior to the study injections are not considered AEs unless the condition recurs after the subject has recovered from the pre-existing condition or the condition worsens in intensity or frequency during the study.

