Subjects will have the option of participating in a Biopsy Sub-study. Participation in the sub-study is voluntary and will not affect the subject's eligibility to participate in the main study. Biopsy samples will be collected from the submental region at Visit B1 and B2. Samples will be collected at 2 timepoints: Visit B1 will occur at least 4 weeks before the first BELKYRA® treatment (at Visit 2.1); Visit B2 will occur 8 weeks after the last BELKYRA® treatment and at least 4 weeks prior to VOLUMA™ treatment (at Visit 4). The initial BELKYRA® treatment (Visit 2.1) will not occur until the initial biopsy site has healed (at least 4 weeks after biopsy); if not healed by 4 weeks, BELKYRA® treatment will be postponed until healed. The VOLUMA™ treatment (Visit 4) will not occur until the second biopsy site has healed (at least 4 weeks after biopsy); if not healed by 4 weeks, VOLUMA™ treatment will be postponed until healed. Histological changes from baseline to after BELKYRA® treatment(s) will be evaluated.

Data will be collected at each clinic visit for all relevant parameters per the *Schedule of Visits and Procedures (Table 1.1)*.

All adverse events (AEs) will be collected from the signing of the informed consent form (Visit 1) through to the last study visit (Visit 6). Serious adverse events (SAEs) will be reported directly to Allergan within the specified time, format, and procedure described in *Section 9: Adverse Events*. Injection site reactions (ISRs) recorded during the VOLUMA™ treatment period will be collected in an ISR Diary as described in *Section 7.1.8: Injection Site Reaction (ISR) Diary*.

Clinical Study Protocol: CMO-MA-FAS-0513

Key Criteria for Inclusion:

1. Male and females 18 to 65 years of age inclusive on the day of initial BELKYRA® treatment
2. Sign the Independent Ethics Committee (IEC)/Institutional Review Board (IRB)-approved informed consent form (ICF) prior to any study-related procedures being performed
3. Grade 2 or above on the ALJDS [REDACTED]
[REDACTED]
[REDACTED]
4. Submental fat graded by the Investigator as 2 or 3 using the CR-SMFRS [REDACTED]
[REDACTED]
[REDACTED]
5. [REDACTED]
[REDACTED]
[REDACTED]
6. [REDACTED]
[REDACTED]
7. [REDACTED]
[REDACTED]
[REDACTED]
[REDACTED]
8. [REDACTED]
[REDACTED]

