9.3 PROCEDURES FOR REPORTING AN SAE

Any SAE occurring during the study period (beginning with informed consent) and through 30 days after study exit must be immediately reported on 2 SAE forms. Both drug and device SAE fax forms must be recorded and faxed to the appropriate numbers on the front page of the protocol. All subjects with an SAE must be followed up and the outcomes reported. The Principal Investigator must supply the Sponsor and the IRB with any additional requested information (e.g., hospital discharge summary, autopsy reports and terminal medical reports) if required. The Sponsor shall evaluate all SAEs for both drug and device. Device SAEs will be documented in writing as to whether they meet the definition of an UADE. These shall be reported to all participating Investigators, the regulatory authorities, and the IRB.

In the event of a serious adverse event, the Investigator must:

1. Notify Allergan immediately (within 24 hours) using the SAE reporting forms (for information see page 1 of the protocol). Emergency phone numbers and relevant Allergan personnel contacts are also on the front page of protocol.

Clinical Study Protocol: CMO-MA-FAS-0513

2. Obtain and maintain in his/her files all pertinent medical records, information, and medical judgments from colleagues who assisted in the treatment and follow-up of the subject.
3. Provide Allergan with a complete, written case history (SAE report form) including copies of supporting reports (e.g., progress notes, laboratory reports) and a statement from the Investigator as to whether the event was or was not related to the use of the investigational drug or device.
4. Promptly inform the governing IRB/IEC of the SAE, if it is device-related, as required by the IEC/IRB, local regulations, and the governing health authorities.

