10.1.1 Analysis Populations

The following analysis populations will be used:

- Full Analysis Set (FAS) – Consists of all subjects who received BELKYRA®
- Evaluable Set (ES) – Consists of subjects in the Full Analysis Set who received BELKYRA® and VOLUMA™ and a post-treatment efficacy assessment at Visit 6 (Exit Visit).
- Safety Analysis Set (SAS) – Consists of all subjects who consented to participation. Includes subjects who are defined as Full Analysis Set as well as subjects who were biopsied but did not receive BELKYRA®

The FAS population will be used for summary of subject disposition, demographics, baseline characteristics and efficacy analyses of endpoints assessed up to end of BELKYRA® treatment; the ES population will be used for the efficacy analyses of endpoints assessed at the final study visit, and the SAS population will be used for safety analyses.

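### The device AE definition takes the study injections, not informed consent, as its cut-off for pre-existing signs, so a first-biopsy complication could be left off the AE eCRF

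*Protocol*

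**What the plan says.** Four places in the Protocol start safety recording at consent:

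- Protocol Summary: "All adverse events (AEs) will be collected from the signing of the informed consent form (Visit 1").
- Section 9: "Throughout the course of the study (from the date of informed consent), all AEs will be monitored and recorded in source documents"; entry in the eCRF is required as well.
- Section 9.1.1.1 (drug): "AEs will be assessed and documented, as appropriate, throughout the study (i.e., after informed consent has been obtained").
- Section 9.3: "Any SAE occurring during the study period (beginning with informed consent") must be reported immediately, up to 30 days after exit.

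Section 9.1.1.2 (device) sets a different reference point for what counts as pre-existing: "Disease signs and symptoms that existed prior to the study injections are not considered AEs unless the condition recurs after the subject has recovered". It has one more exception, where "the condition worsens in intensity or frequency during the study".

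The Safety Analysis Set in Protocol 10.1.1 takes in "subjects who were biopsied but did not receive" BELKYRA. SAP 7.2 calls a post-baseline AE treatment-emergent when no AE with the same system organ class and preferred term was recorded before treatment, or when its severity exceeds the earlier one. The post-baseline period starts with the first BELKYRA treatment.

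**The concern.** Section 9 tells sites to record every AE from consent, but the definitions below it decide what an AE is. If a definition removes signs that were present before injection, the instruction to record from consent does not by itself bring them back.

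The interval matters because it contains a study procedure. Sub-study subjects have tissue excised at Visit B1, and the Protocol Summary foresees sites that have not healed after four weeks. An infection, bleed or slow-healing wound at that site would be harm from the study itself. If it never reaches the eCRF, no later table or listing can recover it.

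**Working it through.** The plan gives no figure on this point to reproduce. The check compares the provisions and adds simple arithmetic for the interval affected.

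**1. Size of the interval.** Inputs: about 10 sub-study subjects and about 50 in total (Protocol 3 and 4.1); first biopsy at least 4 weeks before BELKYRA (Protocol 3.1); Screening and Day 0 may fall on the same day for subjects outside the sub-study (Protocol 3.2).

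- Share exposed: 10 / 50 = 20%.
- Time exposed: 10 × 4 weeks = about 40 subject-weeks as a minimum, since treatment waits for healing.
- Other subjects: from zero up to the time between Screening and Day 0.

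**2. The two provisions applied to a sign that first appears after Visit B1 and before the first injection.**

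| Course of the sign | Recording from consent | 9.1.1.2 read literally |
|---|---|---|
| Resolves before Day 0, no recurrence | AE | Not an AE |
| Persists unchanged past Day 0 | AE | Not an AE |
| Worsens during the study | AE | AE (exception) |
| Resolves, then recurs | AE, both episodes | AE for the recurrence only |

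The provisions disagree in the first two rows and on the first episode in the last row. The exceptions do not reach a first-time complication that resolves without worsening or recurring.

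**3. Whether the drug definition closes the gap.** Section 9.1.1.1 has no such exclusion, and its second paragraph starts documentation after consent. Its opening sentence, however, ties an AE to a subject who has been given a pharmaceutical product, and 9.1.1.2 ties it to use of the device. Before Day 0 a subject has received neither, so neither definition clearly covers a Visit B1 complication.

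**4. Effect on the SAP outputs.** Take the last row, with the recurrence after Day 0 at no higher severity. If the first episode is on file, the rule in SAP 7.2 finds a matching pre-treatment AE and the recurrence is not treatment-emergent. If the first episode is missing, the recurrence is counted as treatment-emergent. In the first two rows the event drops out of the by-subject AE listing. The incidence categories set out in SAP 7.2 are for treatment-emergent events, so an event confined to the time before Day 0 would not enter them in any case.

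**5. Serious events.** Section 9.1.2 defines an SAE as a kind of AE, so read literally the exclusion would carry over. Section 9.3 expressly starts SAE reporting at consent, against that reading.

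**The case against.** The best reply is that the clause is not a second start date. It says what counts as a pre-existing condition, speaks of disease signs, and refers to recovery from that condition. A complication of a study biopsy is a new, procedure-caused event, and a sensible site would record it. The surrounding text supports this. Section 9 follows AEs related to study procedures as well as treatments, 9.1.5 includes study procedures in its causality test, 9.2 requires all AEs to be recorded, and the SAP rule presupposes that pre-treatment AEs are in the database. The clause is also confined to the device subsection, and VOLUMA is not given until Visit 4. The visit sections after 6.1.4, including the one on Visit B1, are redacted and may carry their own AE instruction. Delayed healing would in any case show up as a postponed treatment.

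Most of this stands, and it reduces the likelihood that an event is missed. It does not remove the conflict in wording, because a site applying 9.1.1.2 as written has a stated ground for leaving such an event out.

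A reader might go further and infer that nothing experienced by a subject who is biopsied but never injected could be an AE. The documents do not support that. With no injection, the clause has no clear reference point for such a subject, and both documents deliberately place these subjects in the safety set.

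**Conclusion.** The point holds as an inconsistency of wording with a limited safety consequence. Section 9.1.1.2 does not match the Protocol Summary or Sections 9, 9.1.1.1 and 9.3, and read literally it could keep a first-biopsy complication off the AE eCRF in about 10 subjects over at least about 40 subject-weeks. It could also remove the comparator that the SAP's treatment-emergent rule uses. The primary endpoint and the sample size are unaffected.

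This rests on two assumptions: that a site applies the device clause to events before Day 0, and that the redacted visit text does not already settle the matter.

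Two stronger readings are tempting. One is that biopsy harm will go unrecorded and expedited SAE reports will be missed. The documents support only that an event could be missed, since several explicit instructions point to recording from consent and 9.3 does so for SAEs. The other is that the undefined term for the injections means the VOLUMA injections, so that signs arising during BELKYRA treatment also count as pre-existing. Nothing in the documents restricts the term in that way, and after Day 0 the drug definition in 9.1.1.1 applies without any such exclusion.

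**What to change.** In Protocol 9.1.1.2, replace the reference to the study injections with a reference to informed consent and leave the recurrence and worsening exceptions as they are. Only conditions present at consent are then pre-existing, in line with the Protocol Summary and Sections 9, 9.1.1.1 and 9.3. The site notice should say that new events after consent, including complications of the first biopsy, are recorded as AEs.

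The cost is a one-phrase amendment, the notice and a few more AE entries. The SAP needs no change, because its rule already expects pre-treatment AEs to be on file.

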9.1.1.3 Injection Site Reaction (ISR)

ISRs following treatment with dermal fillers include redness, pain after injection, tenderness to touch, firmness, swelling, lumps/bumps, bruising, itching, discoloration, and other specified events. Subjects will maintain a diary record of the presence, location, frequency, severity, and duration of any ISR for 4 weeks after treatment with VOLUMA™ (initial treatment at Visit 4 and Touch-up at Visit 5, if applicable). (See *Section 7.1.8: Injection Site Reaction (ISR) Diary* for further details).

Subjects will indicate the occurrence of an ISR and severity (none, mild, moderate, severe) of the event. ISRs that persist longer than 4 weeks (i.e., ongoing at the end of the diary period) will be reported as AEs and followed as described in *Section 9.2: Procedure for Reporting Adverse Events*. If an ISR is ongoing or appears 4 weeks after the subject’s last study visit, it will be followed up by Allergan Product Surveillance separate from this study protocol.

Clinical Study Protocol: CMO-MA-FAS-0513

9.1.2 Serious Adverse Events (SAE)

An SAE is any AE occurring at any dose that results in any of the following outcomes: death, a life-threatening AE, subject hospitalization or prolongation of existing hospitalization, a persistent or significant disability/incapacity, or a congenital anomaly/birth defect. Important medical events that may not result in death, be life-threatening, or require hospitalization may be considered an SAE when, based upon appropriate medical judgment, they may jeopardize the subject and may require medical or surgical intervention to prevent one of the outcomes listed in this definition. (See *Section 9.3: Procedures for Reporting an SAE*).

Note: Allergan considers all cancer AEs as SAEs. In addition, Allergan considers any abortion (spontaneous or not spontaneous) as an SAE.

9.1.3 Unanticipated Adverse Device Effects (UADE)

An Unanticipated Adverse Device Effect (UADE) is any device-related SAE that meets one or more of the following criteria:

- Is not identified in nature, severity, or frequency in current literature on the product
- Is life-threatening, even if temporary in nature
- Results in permanent impairment of a body function or permanent damage to a body structure
- Necessitates medical or surgical intervention to preclude permanent impairment of a body function or permanent damage to a body structure.

Also considered an UADE is any device malfunction that would be likely to cause or contribute to a death or serious injury if the malfunction were to recur. The Investigator will notify the Allergan Medical Affairs Department within 24 hours of any device malfunction and the Clinical Research representative will provide instruction for the return of any faulty syringe for evaluation.

As required by United States (US) Code of Federal Regulation (CFR) 21 §812.46(b)(2), if the Sponsor determines that an UADE presents an unreasonable risk to study subjects, the Sponsor will terminate the investigation within 5 working days of the unreasonable risk determination.

